11.6 Interim Analysis

No interim analysis is planned.

12 STUDY MANAGEMENT

12.1 Monitoring

The investigator will be responsible for preparing and maintaining adequate and accurate source documents (medical records, ECGs, raw data collection forms, etc.) designed to record all observations and other pertinent data for each subject treated with the study drug. The investigator will allow representatives of the Sponsor, contract designees, authorized regulatory authority inspectors, and the Institutional Review Board (IRB)/Independent Ethics Committee (IEC) to have direct access to all documents pertaining to the study. The investigator is to immediately notify the Sponsor of any regulatory authority inspections. The investigator will be informed about the outcome of any Sponsor audit.

This study will be monitored regularly, by or under supervision of a monitor from the Sponsor. The frequency of monitoring visits will be agreed upon by the Sponsor's representative and the study site.

Monitoring visits will take place on a regular basis according to the enrollment rate and number of subjects enrolled at each investigational site. During these visits, the monitor will check the completion of the eCRF entries, compliance with the study protocol and with Good Clinical Practice - International Conference on Harmonization (GCP-ICH), and their agreement with the source data. The monitor will also verify the correct use of the study drug. At a final visit, the monitor will check all remaining material including the remaining quantities of the study drug and will organize their return to the Sponsor or designee. At each visit, the investigator and staff will be expected to cooperate with the Sponsor's representative(s) for the purposes of review and verification of protocol compliance, AE reporting, eCRFs, source documents, clinical supplies and inventory records, and any additional records as may have been previously arranged between the investigator and the Sponsor's representative(s).

The investigator and/or other designated study personnel are expected to contact the Sponsor with any study concerns and/or questions. Contact information is provided in the Study Reference Manual for the site.

12.2 Protocol Amendments

The Sponsor may propose to amend this protocol at any time.

No change to the protocol will be implemented until the Sponsor and the IRB/IEC have reviewed and approved the amendment.

In the event of an emergency, the investigator shall implement any medical procedures deemed appropriate for subject safety. All such procedures must have written documentation and be promptly reported to the Sponsor.

12.3 Protocol Deviations

A protocol deviation is any change, divergence, or departure from the IRB/IEC approved protocol (intentional or unintentional). Protocol deviations are to be reported to the IRB/IEC according to the IRB/IEC guidelines.

12.4 Withdrawal of Subjects

Withdrawn subjects are those who do not complete all evaluations and procedures outlined in the protocol. Subject withdrawal requires a 2-week dose taper. A subject will be considered to have discontinued prematurely if he/she withdraws prior to completing Visit 8 (Final Visit). If a subject misses 7 consecutive days AND has taken less than 80% of their doses of study medication in a 42-day (6-week) period, then the subject must be discontinued. Subjects may also be withdrawn from the study because of any of the following:

- **Adverse Event:** An AE that, in the opinion of the investigator or Sponsor, suggests that continued participation in the study is not in the subject's best interest for safety reasons (also see [Section 10](#)). All AEs that are present when the subject withdraws from the study will be followed as described in [Section 9.7.4](#).
- **Medical Condition:** Any medical condition that, in the investigator's judgment, would increase the risk or interfere with the evaluation of study objectives.
- **Lost to Follow-up:** Confirmed at minimum by two phone calls and a traceable letter without answer.
- **Subject Request:** Subject requests for any reason to be withdrawn or withdraws his/her consent. Every effort should be made to determine the reason for the withdrawal request (e.g., AE, lack of efficacy, scheduling issues, etc.).
- **Protocol Deviation:** A subject may be withdrawn from the study at the discretion of the investigator or Sponsor due to poor compliance with protocol requirements that may compromise the study results or subject safety.
- **Enrollment in Another Study:** Enrollment in other protocols involving research drugs, medical devices, or surgeries.
- **Other Anti-spasticity Treatment:** Starting any other pharmacological anti-spasticity treatment during the study.

- **Relapse:** Subjects who experience an acute MS exacerbation/relapse (symptoms including but not limited to visual disturbance, dizziness, tingling, or extreme fatigue lasting greater than 24 hours and occurring at least 30 days after a previous relapse) requiring immediate therapy or adjustment in disease-modifying medication dose (e.g., oral or intravenous high-dose steroid therapy).
- **Other:** Other reasons include but are not limited to: Investigator decision that it is in the subject's best interest to be withdrawn, administrative reasons, relocation of subject, etc. If a subject or the partner of a subject becomes pregnant during the study, the subject will be withdrawn from the study and followed through conclusion of the pregnancy (see [Section 9.7.5](#)).

When possible, a decision to discontinue a subject from the study should first be discussed with the Sponsor's Medical Monitor. If a subject is prematurely discontinued after randomization and prior to the final scheduled visit, every effort should be made to perform all of the Visit 8 assessments (Table 1). The reason(s) for early withdrawal must be recorded in the eCRF. Subjects withdrawn from the study will not be replaced.

12.5 Termination of the Study

The study may be terminated at any time at the request of the Sponsor or a regulatory authority, with proper and timely notification of all parties concerned. The IRB/IEC will be informed promptly and the Sponsor or the investigator will supply reason(s) for the termination or suspension, as specified by the applicable regulatory requirements. Otherwise, the study is considered terminated upon completion of all subject treatments and evaluations.

12.6 Publication Policy

The data obtained in this study are the property of the Sponsor, who will make reasonable efforts to assure that the results are published in a peer-reviewed journal. As some of the information concerning the investigational product and development activities at the Sponsor may be of a strictly confidential nature, any manuscript or other presentation of data must first be reviewed by the Sponsor before its submission.

13 ETHICS

13.1 Conduct of the Study

This study will be conducted in accordance with the ICH Harmonized Tripartite Guideline for GCP, 1997; the US Title 21 CFR parts 50, 56, and 312; and the ethical principles that have their origin in the Declaration of Helsinki. The study will not begin until all of the requirements of the appropriate regulatory authorities have been fulfilled.

13.2 Institutional Review Boards and/or Independent Ethics Committees

This protocol (and any changes), all consent forms, and subject consent procedures must be reviewed and approved by a properly constituted IRB/IEC. The information presented to the IRB/IEC at the time initial approval is sought must include any plans for subject recruitment that

involve advertising or other direct contact with potential subjects outside of the doctor-subject relationship. A letter of approval issued by the IRB/IEC must be sent to the Sponsor prior to initiation of the study. Any changes made to the protocol must be approved by the IRB/IEC prior to implementation, except where needed to eliminate a potential imminent safety hazard to the subject. In this case, immediate implementation may take place followed by IRB/IEC approval. Review and approval by the IRB/IEC for continuation of the study must take place at least once a year.

13.3 Written Informed Consent

The investigator or designee will explain the nature of the study, its purpose and associated procedures, the expected duration, and the potential benefits and risks of participation to each subject prior to his/her entry into the study (i.e., before examinations and procedures associated with selection for the study are initiated). Each subject will have ample opportunity to ask questions and will be informed about the right to withdraw from the study at any time without any disadvantage and without having to provide reasons for this decision.

Following this informative discussion, the subject will be asked if he/she is willing to sign a statement of informed consent. Only subjects who voluntarily sign the ICF may enter the study. The ICF must be reviewed and approved by the Sponsor and the IRB/IEC prior to its use.

The original signed ICF will remain in the investigator's files. The investigator or designee will indicate in each subject's source documents that he/she has informed the subject about the study and its procedures, the subject has signed and dated the ICF, and the subject has been given a copy of the signed ICF. The investigator or designee will inform subjects of any new information that may be relevant to the subject's willingness to continue in the study.

13.4 Subject Confidentiality

The Sponsor ensures that the following have permission to review all study-related documents: monitor, auditor, IRB/IEC, and regulatory authorities. The subject's identity and study-related records will remain confidential throughout the duration of the study data collection and reporting process.

A unique subject identification code will be assigned to each potential study subject. The identification code protects the subject's identity and is used in lieu of the subject's name when reporting subject data. The data will always maintain the confidentiality of the subject.

The investigator or designee will review the subject data, which will be referenced using the subject identifier. At the conclusion of the study, the data obtained may be presented to regional regulatory authorities but the subject's identity will not be revealed. In addition, if any clinical data obtained from the study are published in scientific journals or presented at scientific meetings, the subject's identity will not be revealed.

13.5 Records Retention

The investigator must maintain essential study documents (protocol and amendments, source documentation corresponding to all information contained in the eCRFs, signed ICFs, relevant

correspondence, and all other supporting documentation) until at least 2 years after the last approval of a marketing application in an ICH region and until there are no pending or contemplated marketing applications in an ICH region, or at least 2 years after the formal discontinuation of clinical development of the investigational product. These documents should be retained for a longer period if required by the applicable regulatory requirements or the hospital, institution, or private practice in which the study is being conducted. Subject identification codes (subject names and corresponding study numbers) will be retained for this same time period. Custody of the records may be transferred to another responsible party, acceptable to the Sponsor, who agrees to abide by the retention policies. Written notice of transfer must be submitted to the Sponsor. The investigator must contact the Sponsor prior to disposing of any study records.

13.6 Financing

Funding for this study will be agreed between the investigator and the Sponsor and will be confirmed in writing before the study starts.

Completion of Financial Disclosure Forms will be required before the study starts. Any additions to the primary site personnel will necessitate the completion of new Financial Disclosure Forms. This information will also be collected at site closure and 1 year after the completion of the study.

14 QUALITY CONTROL AND QUALITY ASSURANCE

The Sponsor and investigator will take all steps possible to ensure the accuracy, consistency, completeness, and reliability of the data, including participating in an investigator meeting and/or site initiation visit, routine site monitoring, review of eCRFs against source documents, and quality control checks.

In addition, a representative from the Sponsor's Clinical Quality Assurance Department may conduct periodic audits of the study processes, including, but not limited to, auditing the clinical site, laboratories, vendors and CROs, the clinical database, and the final study report.

15 DATA HANDLING AND RECORD KEEPING

This study will use web-based eCRFs developed through a validated, Electronic Records/Electronic Signatures-compliant platform (US Title 21 CFR Part 11). The Sponsor's Clinical Data Management department or designee will create the eCRFs and corresponding clinical database based on the final protocol.

All site personnel who will be using this system will receive formal training on the system, after which each person will be issued a unique username and password. Only the person who owns the username and password will enter the system using that username and password. For data security reasons and to be in compliance with regulatory guidelines, usernames and passwords are not transferable.

The investigator is responsible for all data entered via the remote data capture (RDC) system eCRFs and must confirm the accuracy of the data by electronically approving (signing) the eCRFs. This responsibility includes the timely completion and accuracy of the data entered into the eCRFs by their site personnel as well as the review and approval of some data entered directly into the

database (e.g., clinical laboratory results) by an external vendor. The Sponsor will review the database to identify data errors or inconsistencies, which will be posted in the RDC system as queries for resolution. In addition, the Sponsor may make obvious corrections to the data in the database (e.g., obvious errors in dates).

Appendix 1. Modified Ashworth Scale

Score	Modified Ashworth Scale
0	No increase in muscle tone
1	Slight increase in muscle tone, manifested by a catch and release or by minimal resistance at the end of the range of motion when the affected part(s) is moved in flexion or extension /abduction or adduction, etc.
1+	Slight increase in muscle tone, manifested by a catch, followed by minimal resistance throughout the remainder (less than half) of the ROM (range of movement).
2	More marked increase in muscle tone through most of the ROM, but affected part(s) easily moved.
3	Considerable increase in muscle tone, passive movement difficult.
4	Affected part(s) rigid in flexion or extension (abduction or adduction, etc.)

Source: [Bohannon and Smith 1987](#)

Scoring: (Total Numeric-transformed mAS score)

Ashworth Score	0	1	1+	2	3	4
	↓	↓	↓	↓	↓	↓
Numerical Score	0	1	2	3	4	5

Numerical Score

Upper Extremities:

Shoulder

Elbow

Wrist

Numerical Total:

R	L

Lower Extremities:

Hip

Knee

Ankle

Numerical Total:

R	L

Appendix 2. Expanded Disability Status Score

0.0	Normal neurological exam (all grade 0 in all Functional System [FS] scores*).
1.0	No disability, minimal signs in one FS* (i.e., grade 1).
1.5	No disability, minimal signs in more than one FS* (more than 1 FS grade 1).
2.0	Minimal disability in one FS (one FS grade 2, others 0 or 1).
2.5	Minimal disability in two FS (two FS grade 2, others 0 or 1).
3.0	Moderate disability in one FS (one FS grade 3, others 0 or 1) or mild disability in three or four FS (three or four FS grade 2, others 0 or 1) though fully ambulatory.
3.5	Fully ambulatory but with moderate disability in one FS (one grade 3) and one or two FS grade 2; or two FS grade 3 (others 0 or 1) or five grade 2 (others 0 or 1).
4.0	Fully ambulatory without aid, self-sufficient, up and about some 12 hours a day despite relatively severe disability consisting of one FS grade 4 (others 0 or 1), or combination of lesser grades exceeding limits of previous steps; able to walk without aid or rest some 500 meters.
4.5	Fully ambulatory without aid, up and about much of the day, able to work a full day, may otherwise have some limitation of full activity or require minimal assistance; characterized by relatively severe disability usually consisting of one FS grade 4 (others 0 or 1) or combinations of lesser grades exceeding limits of previous steps; able to walk without aid or rest some 300 meters.
5.0	Ambulatory without aid or rest for about 200 meters; disability severe enough to impair full daily activities (e.g., to work a full day without special provisions); (Usual FS equivalents are one grade 5 alone, others 0 or 1; or combinations of lesser grades usually exceeding specifications for step 4.0).
5.5	Ambulatory without aid for about 100 meters; disability severe enough to preclude full daily activities; (Usual FS equivalents are one grade 5 alone, others 0 or 1; or combination of lesser grades usually exceeding those for step 4.0).
6.0	Intermittent or unilateral constant assistance (cane, crutch, brace) required to walk about 100 meters with or without resting; (Usual FS equivalents are combinations with more than two FS grade 3+).
6.5	Constant bilateral assistance (canes, crutches, braces) required to walk about 20 meters without resting; (Usual FS equivalents are combinations with more than two FS grade 3+).
7.0	Unable to walk beyond approximately 5 meters even with aid, essentially restricted to wheelchair; wheels self in standard wheelchair and transfers alone; up and about in wheelchair some 12 hours a day; (Usual FS equivalents are combinations with more than one FS grade 4+; very rarely pyramidal grade 5 alone).

7.5	Unable to take more than a few steps; restricted to wheelchair; may need aid in transfer; wheels self but cannot carry on in standard wheelchair a full day; May require motorized wheelchair; (Usual FS equivalents are combinations with more than one FS grade 4+).
8.0	Essentially restricted to bed or chair or perambulated in wheelchair, but may be out of bed itself much of the day; retains many self-care functions; generally has effective use of arms; (Usual FS equivalents are combinations, generally grade 4+ in several systems).
8.5	Essentially restricted to bed much of day; has some effective use of arm(s); retains some self-care functions; (Usual FS equivalents are combinations, generally 4+ in several systems).
9.0	Helpless bed patient; can communicate and eat; (Usual FS equivalents are combinations, mostly grade 4+).
9.5	Totally helpless bed patient; unable to communicate effectively or eat/swallow; (Usual FS equivalents are combinations, almost all grade 4+).
10.0	Death due to MS.

EDSS = expanded disability status scale; FS = Functional System

* Excludes cerebral function grade 1.

Note 1: EDSS steps 1.0 to 4.5 refer to patients who are fully ambulatory and the precise step number is defined by the FS score(s). EDSS steps 5.0 to 9.5 are defined by the impairment to ambulation and usual equivalents in FS scores are provided.

Note 2: EDSS should not change by 1.0 step unless there is a change in the same direction of at least one step in at least one FS.

Appendix 3. Patient Global Impression of Change Scale

PATIENT'S GLOBAL IMPRESSION OF CHANGE (PGIC) SCALE

Date _____ Patient Name _____ Date of Birth _____

Chief Complaint (Presenting Problem): _____

Since beginning treatment at this clinic, how would you describe the change (if any) in ACTIVITY LIMITATIONS, SYMPTOMS, EMOTIONS, and OVERALL QUALITY OF LIFE, related to your painful condition? Please circle the number below, that matches your degree of change since beginning care at this clinic for the above stated chief complaint.

No change	Almost the same	A little better	Somewhat better	Moderately better	Better	A great deal better
1	2	3	4	5	6	7

Explanation:

- 1 = No change (or condition has got worse)
- 2 = Almost the same, hardly any change at all
- 3 = A little better, but no noticeable change
- 4 = Somewhat better, but the change has not made any real difference
- 5 = Moderately better, and a slight but noticeable change
- 6 = Better, and a definite improvement that has made a real and worthwhile difference
- 7 = A great deal better, and a considerable improvement that has made all the difference

[figure not shown]
Patient's signature: X _____

[figure not shown]
Do not write in this box - FOR OFFICE USE ONLY.

[figure not shown]
NOTE TO HEALTH CARE PROVIDER

[figure not shown]
A significant, favorable change is a score of 5- 7
No significant change is a 1-4 response.
Note, this is a dichotomous scale (5-7 = yes; 1-4 = no).
A 2-point change is significant from their last reported score.
Reference: Hurst H, Bolton J. Assessing the clinical significance of change scores recorded on subjective outcome measures. Journal of Manipulative Physiological Therapeutics (JMPT) 2004;27:26-35.

[figure not shown]

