- Collect unused study medication, assess compliance, and study drug accountability ([Section 7.9](#)).
- Record any AEs that have occurred ([Section 9.7](#)).
- Record all concomitant medications/therapies the subject is currently taking ([Section 7.7](#)).
- Schedule the next study visit.

6.5 Visit 7 End of Taper (Telephone Visit) – Week 56

- Record any AEs that have occurred ([Section 9.7](#)).
- Record all concomitant medications/therapies the subject is currently taking ([Section 7.7](#)).
- Schedule the final study visit.

6.6 Visit 8 (Final Visit or Early Termination) – Week 60

The assessments/procedures listed for Visit 8 (Final Visit) are to be completed by all subjects regardless of whether they complete the entire study or prematurely withdraw from the study. If the Final Visit is performed before Week 60 due to early termination of the subject, every effort should be made to perform the clinical evaluations as follows, especially blood sampling for hematology and serum chemistry, urinalysis, ECG, and the 2-week study drug taper. Assessments/procedures will include the following:

- Record weight ([Section 9.4](#)).

- Record vital sign measurements, including BP, heart rate, respiratory rate, and body temperature (Section 9.2).
- Collect blood and urine samples for hematology, serum chemistry, and urinalysis (Section 9.5). Subject should be fasting if possible.
- Perform a standard 12-lead ECG (Section 9.6.1).
- Collect a urine sample for pregnancy testing for women of childbearing potential (Section 7.8).
- Administer the C-SSRS (Section 9.6.3).
- Perform the TNmAS-MAL assessment (Section 8.2).
- Administer the EDSS assessment (Section 8.3).
- Administer the PGIC questionnaire (Section 8.1).
- Administer the USP questionnaire (Section 9.6.2).
- Collect unused study medication, assess compliance, and study drug accountability (Section 7.9).
- Record any AEs that have occurred (Section 9.7).
- Record all concomitant medications/therapies the subject is currently taking (Section 7.7).

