8 EFFICACY ASSESSMENTS

8.1 Patient Global Impression of Change

The PGIC is a standard instrument that is a well validated outcome measure. The 7-point PGIC measures change in the subject's overall status using the following categorical scale:

- 1 = Very much improved
- 2 = Much improved
- 3 = Improved
- 4 = No change
- 5 = Minimally worse
- 6 = Much worse
- 7 = Very much worse

The PGIC will be completed at the visits specified in Table 1. The PGIC is provided in Appendix 3.

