11.4 Efficacy Analyses

11.4.1 Efficacy Endpoints

11.4.1.1 Patient Global Impression of Change

Descriptive summaries for PGIC scores will be tabulated by study visit and for change from baseline.

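### Protocol Section 8.1 and the Appendix 3 form it cites are different PGIC scales running in opposite directions, and the SAP does not say which applies

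*Protocol*

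**What the plan says.** Assessing the PGIC over 1 year is a stated secondary objective (Protocol 3.2, SAP 4.1.2).

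- **Protocol 8.1** lists seven codes from "1 = Very much improved" through 4 (no change) to "7 = Very much worse", and describes the rating as one of overall status. It ends with "The PGIC is provided in Appendix 3".
- **Protocol Appendix 3** prints a form whose codes start at "1 = No change (or condition has got worse") and end at "7 = A great deal better, and a considerable improvement that has made all the difference". Its note to the provider says "A significant, favorable change is a score of 5- 7" and treats 1-4 as no significant change. The question concerns a painful condition, with the start of care at the clinic as its reference point.
- **Protocol 6.2 and 6.6** tell sites "Administer the PGIC questionnaire (Section 8.1"), which leads on to Appendix 3.
- **Protocol 11.4.1.1** plans the analysis: "Descriptive summaries for PGIC scores will be tabulated by study visit and for change from baseline".
- **SAP 5.3** refers to protocol Section 8 for details of the efficacy variables. **SAP 9.2** plans PGIC frequencies, percentages and descriptive statistics by visit, without category labels, direction or a recoding rule.

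**The concern.** The text and the form it names cannot both be the instrument. A site following Section 8.1 reaches the Appendix 3 form. An analyst following SAP 5.3 reaches the Section 8.1 labels. If numbers from the form are then decoded with those labels, improvement is tabulated as worsening for a secondary objective. No hypothesis tests are planned (SAP 7.4.1), so the labelled table is the whole PGIC result, and no other PGIC output would expose the error.

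A second problem remains even if the labels are right. On the Appendix 3 form a subject who has worsened has only code 1 to mark, and shares it with subjects who have not changed. The only post-baseline PGIC in Protocol Table 1 is at Visit 8, Week 60. That is 60 - 56 = 4 weeks after the taper ends, a point at which worsening needs to be measurable.

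**Working it through.** The plan states no figure that depends on this point, so there is none to reproduce. The check sets the two scales side by side.

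**Step 1. Labels by code** (shortened; Protocol 8.1 and Appendix 3). The class columns group Section 8.1 as improved (1-3), no change (4) and worse (5-7), and group Appendix 3 by its own key.

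| Code | Section 8.1 | Class | Appendix 3 | Class by its key |
|---|---|---|---|---|
| 1 | very much improved | improved | no change or worse | not significant |
| 2 | much improved | improved | almost the same | not significant |
| 3 | improved | improved | a little better | not significant |
| 4 | no change | no change | somewhat better | not significant |
| 5 | minimally worse | worse | moderately better | favorable |
| 6 | much worse | worse | better | favorable |
| 7 | very much worse | worse | a great deal better | favorable |

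Labels that differ: 7 of 7.

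**Step 2. Codes that change class** when an Appendix 3 score is given its Section 8.1 label. Codes 1, 2 and 3 go from not significant to improved (3 codes). Codes 5, 6 and 7 go from favorable to worse (3 codes). Code 4 stays. Total: 3 + 3 = 6 of 7.

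Grouping by plain wording instead of the form's key, code 3 is the one that keeps its broad meaning (some improvement on both) and code 4 does not. The count is again 6 of 7. Under both groupings codes 5-7 are reversed.

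**Step 3. Effect on the table.** Let p, q and r be the shares of subjects marking 5-7, 4 and 1-3 on Appendix 3, with p + q + r = 1. Under Section 8.1 labels the table would show worse = p, no change = q, improved = r. The whole favorable share p is reported as worse and none of it as improved. A subject who actually worsened marks code 1 and would be reported in the best category.

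**Step 4. Sign of change from baseline** (post-baseline minus baseline, SAP 7.4.1). On Section 8.1 a two-step improvement from 4 is 2 - 4 = -2. On Appendix 3 it is 6 - 4 = +2. The sign depends on which form was used.

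**Step 5. Can the scores be reversed afterwards?** Under 8 - x the favorable codes 5, 6 and 7 become 3, 2 and 1, which are improvement codes. The lower end fails: 8 - 1 = 7 turns no change or worse into very much worse, and 8 - 2 = 6 turns almost the same into much worse. Since Appendix 3 puts no change and all worsening into code 1, no recoding can recover the Section 8.1 worsening categories.

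**The case against.** Several points on the other side are fair.

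- **The reversal is conditional.** It needs Appendix 3 numbers and Section 8.1 labels to meet in the database. The eCRF labels are not in the documents, and the form prints its words beside its numbers. This stands: the contradiction is certain, the mislabelling only possible.
- **The SAP is not wholly silent.** SAP 5.3 points to protocol Section 8, where 8.1 prints labels. But 8.1 itself names Appendix 3 as the instrument, so the pointer returns the analyst to the conflict.
- **The sign flip may never be printed.** SAP 9.2 plans change from baseline for TNmAS-MAL, TNmAS-TL and EDSS, not for PGIC. That is correct, but Protocol 11.4.1.1 still calls for it, and SAP 3.3 says that the SAP analyses are consistent with the protocol.
- **The 6-of-7 count depends on the grouping.** It does, in which code survives. The firm facts are 7 of 7 labels differing and codes 5-7 reversed.
- **The number of ratings differs by document.** SAP Table 1, in a plan that cites protocol Amendment 1, also schedules a PGIC at Visit 4. This adds a visit to the affected output and does not weaken the point.
- **It is only a descriptive secondary endpoint.** True, and this limits the severity.

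**Conclusion.** The concern holds. The protocol gives two incompatible definitions of one secondary endpoint, and the SAP does not choose between them. All 7 labels differ, and the three favorable codes on the form are the three worsening codes in the text. If the form's scores are given the text's labels, 6 of 7 codes change class under the grouping shown and the whole favorable share is reported as worse. That consequence assumes the two are mixed, which the documents neither show nor rule out.

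If one form and its own labels are used throughout, the PGIC remains readable. On Appendix 3, however, worsening cannot be separated from no change. The primary safety objective, TNmAS-MAL and EDSS are unaffected. This should be fixed before the PGIC is tabulated.

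**What to change.** 1. Confirm which form the eCRF carries and which form Study OS440-3004 used at Visit 6.
2. Make Section 8.1 and Appendix 3 the same instrument. The two-sided scale is preferable because it can record worsening, subject to the answer on OS440-3004. Word it for overall status in MS spasticity. Review the code 3 label at the same time: it carries no qualifier, while code 5 is minimal worsening.
3. Define the reference point for post-baseline ratings, and state separately what the Baseline PGIC refers to. For rollover subjects it is the value carried over from OS440-3004 Visit 6. For de novo subjects, reconcile the protocol, which schedules a Baseline PGIC, with SAP Table 1 footnote 6, which says it is not done.
4. Align the eCRF labels, and state category labels and direction in SAP 9.2. State there whether PGIC change from baseline will be tabulated, so that the SAP and Protocol 11.4.1.1 agree.
5. Tabulate data already collected on Appendix 3 under that form's labels. Do not pool or reverse-score them into Section 8.1 codes, and report that worsening could not be separated from no change.

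**Cost.** One appendix page, the eCRF labels and a few SAP sentences, plus the Sponsor and IRB/IEC review that any protocol change requires (Protocol 12.2 and 13.2). Appendix 3 data already collected need a separate table. If OS440-3004 used the other form, rollover Baseline values cannot be compared directly with Visit 8 values.
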